### **13.5.1. Multiplicity Adjustment for Primary and Key Secondary Endpoints**

The statistical comparisons for the primary and the key secondary endpoints will be carried out using a fixed-sequence procedure which tests hypotheses in a hierarchical order to control the familywise type I error rate. This means that statistically significant results for the comparison in the higher rank (primary) for no difference between SAGE-718 versus placebo is required to initiate the testing of the next comparison in the lower rank (key secondary) for no difference between SAGE-718 versus placebo. The hierarchical testing of key secondary endpoints will follow the order shown in Section 6. Details will be provided in the study SAP. Since a hierarchical procedure is used, each comparison will be tested at a significance level of 0.05 and an overall alpha level of 0.05 will be preserved.

## **13.6. Safety Analyses**

Safety and tolerability of SAGE-718 will be evaluated by the frequency of TEAEs and change from baseline in vital signs, clinical laboratory analytes, ECGs, [REDACTED].

[REDACTED] Safety data will be listed by participant and summarized by treatment group, maximum severity and relationship to IP. Vital signs, laboratory parameters, ECGs, [REDACTED] data will be listed by participant and summarized by treatment group. All safety summaries will be performed on the Safety Set.

### **13.6.1. Adverse Events**

AEs/SAEs will be coded using Medical Dictionary for Regulatory Activities (MedDRA) Version 22.0 or higher. A TEAE is defined as an AE with onset after the first dose of IP. The analysis of AEs will be based on the concept of TEAEs. The incidence of TEAEs will be summarized by System Organ Class (SOC) and Preferred Term (PT). In addition, summaries will be provided by intensity (mild, moderate, severe) and by causality (related, not related) to IP.

Any TEAEs leading to discontinuation of treatment or withdrawal from the study and any treatment emergent SAEs will be summarized.

All AEs and SAEs (including those with onset or worsening before the start of IP) through the end of the study will be listed.

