### 12.2.5. Recording Adverse Events

Adverse events spontaneously reported by the participant and/or in response to an open question from the study personnel or revealed by observation will be recorded during the study at the investigational site. The AE term should be reported in standard medical terminology when possible. For each AE, the investigator will evaluate and report the onset (date and time), resolution (date and time), intensity, causality, action taken, outcome and seriousness (if applicable), and whether or not it caused the participant to discontinue the IP or withdraw early from the study.

Intensity will be assessed according to the following scale:

- Mild: symptom(s) barely noticeable to participant or does not make participant uncomfortable; does not influence performance or functioning; prescription drug not ordinarily needed for relief of symptom(s)
- Moderate: symptom(s) of a sufficient severity to make participant uncomfortable; performance of daily activity is influenced; participant is able to continue in study; treatment for symptom(s) may be needed
- Severe: symptom(s) cause severe discomfort; symptoms cause incapacitation or significant impact on participant’s daily life; severity may cause cessation of treatment with IP; treatment for symptom(s) may be given and/or participant hospitalized

It is important to distinguish between serious and severe AEs. Severity is a measure of intensity whereas seriousness is defined by the criteria under Section 12.2.2. An AE of severe intensity may not necessarily be considered serious.

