## 8. STATISTICAL ANALYSIS

### 8.1. General Considerations

Continuous data will be summarized in terms of the number of participants, mean, standard deviation (SD), minimum, and maximum. The minimum and maximum will be reported to the same number of decimal places as the raw data recorded in the database. The mean and median will be reported to one more decimal place, and the SD (and the standard error [SE], if applicable) will be reported to two more decimal places than the raw data recorded in the database. In general, the maximum number of decimal places reported will be four for any summary statistic. Any values that require transformation to standard units (metric or SI) will be converted with the appropriate corresponding precision.

Categorical data will be summarized in terms of the number of participants providing data at the relevant time point (n), frequency counts and percentages. Percentages will be reported to one decimal place unless otherwise specified. Any planned collapsing of categories will be detailed in the SAP text and the data displays.

Percentages will not be presented for zero counts. Percentages will be calculated using the number of participants (n) in the respective analysis set and/or in specific treatment group as the denominator. A missing category shall be included only for categorical variables where no data is available. The missing category will be omitted if there are no missing values for that variable.

For the laboratory results that are “ $\leq x$ ” or “ $\geq x$ ”, where x is a number as collected in the data, the numeric part of the result will be used in the calculation in the summary tables. If a laboratory value contains ‘y <’ then y minus 0.1 for values measured to the first decimal place, 0.01 for values measured to the second place, 0.001 for values measured to the third decimal place, and so on, will be used for the analysis. If a laboratory value contains ‘z >’ then z plus 0.1 for values measured to the first decimal place, 0.01 for values measured to the second place, 0.001 for values measured to the third decimal place, and so on, will be used for the analysis. The same is true if the result is presented as below limit of quantification (BLQ) and a lower limit of quantification (LLOQ) value is provided – LLOQ value will be used for calculation in the summary tables. The actual results as collected will be displayed in the listings.

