**Table 14. [REDACTED]**

#### 8.4.1. Adverse Events

Adverse events will be coded using Medical Dictionary for Regulatory Activities (MedDRA) Version 25.1. Intensity/severity and relationship of AE will be evaluated by the investigator.

A TEAE is defined as an AE with onset on or after the first dose of IP or any worsening of a pre-existing medical condition/AE with onset after the start of IP and throughout the study. The analysis of AEs will be based on the concept of TEAEs. Where the AE start date is missing, adverse events will be assumed to be treatment-emergent, unless there is clear evidence (through comparison of partial dates) to suggest that the adverse event started prior

to the first dose of study treatment. Missing or partial dates will be imputed for AE. The algorithm for missing or partial start /end date is documented in [Appendix C](#).

Adverse events are assigned an AE period based on the onset date/time. AE periods are defined as follows:

- Pre-treatment AE: AE onset date before first IP dosing date/time
- TEAE: AE onset date/time on or after the first IP dose date/time (If an AE start date same as IP first dose date, but no time either in AE start or treatment start, then consider this AE to be in treatment period TEAE.)
- On-treatment TEAE: AE onset date/time on or after first IP dose date/time and on or before IP last dose date + 30 days (Note that time does not matter for the end of this period. i.e. if AE occurred after the last dose but on the same date of last dose, it is considered as on-treatment TEAE)
- Post-treatment TEAE: AE onset date on or after IP last dose date + 31 days

An overall summary of TEAEs will include the number and percentage of participants and number of events in the following categories:

- Any TEAEs
- Any TEAEs (On-treatment, Post-treatment)
- TEAEs by maximum Severity (severe>moderate>mild)
- Any related TEAEs
- Any related TEAEs by maximum Severity (severe>moderate>mild)
- Any serious TEAEs
- Any serious related TEAEs
- Any TEAEs leading to death
- Any TEAEs leading to IP dose reduction
- Any TEAEs leading to IP withdrawal
- Any TEAEs leading to withdrawal from the study
- Any TEAEs leading to IP interruption

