Incidence of TEAEs in following categories will be provided by SOC and PT. A participant is counted only once under each SOC and PT in case of multiple occurrences of the same AE. These tables will be sorted by decreasing frequency of System Organ Class (SOC) in SAGE-718 group, then in placebo group, then alphabetically first within SOC then within preferred term.

- TEAEs
  - On-treatment TEAEs
  - Post-treatment TEAEs

- TEAEs by maximum Severity
  - On-treatment TEAEs
  - Post-treatment TEAEs
- TEAEs by relationship (related, not related) to IP
  - On-treatment TEAE
  - Post-treatment TEAE
- TEAEs by maximum Severity and relationship (related, not related) to IP
  - On-treatment TEAE
  - Post-treatment TEAE
- Serious TEAEs
- TEAEs leading to IP dose reduction
- TEAEs leading to IP withdrawal
- TEAEs leading to withdrawal from the study
- TEAEs leading to IP interruption

Additionally, incidence of TEAEs will be summarized by PT. Most common TEAEs reported >5% in either treatment group will also be summarized by PT.

For maximum severity, participants will be counted only once within each SOC and PT at the maximum severity in the following order: severe > moderate > mild; an AE with missing severity will be omitted from severity presentation and will not be imputed. For relationship to IP, participant will be counted only once within each SOC and PT at the strongest relationship to IP in the following order: related > not related; an AE with relationship missing is treated as related. For seriousness, an AE with missing seriousness will not be imputed. The incidences will be presented by descending frequency of SOC and then, within a SOC, by descending frequency of PT based on the participant count, and in alphabetical order of PT if the incidence within a PT is a tie.

In addition, TEAE summary by SOC and PT will also be presented by the following subgroups:

- Age group: ≤50, >50 years
- Race (Black or African American, White, Other)
- Sex (Male, Female, Unknown/Undifferentiated)
- BMI ( $\leq 18.4$ , 18.5-24.9, 25-29.9,  $\geq 30$  kg/m^2)
- Country (US, Rest of World)

A by-participant listing of each TEAE category will also be provided. All AEs and SAEs (including those with onset or worsening before the start of IP) through the end of the study, and most frequent (5%) TEAE will be listed.

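### TEAEs with missing severity are left out of the severity tables, so displayed maximum severity can be understated and the severity rows need not add up to the TEAE total

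*Protocol*

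**What the plan says.** Protocol section 13.6.1 commits to these tables: "In addition, summaries will be provided by intensity (mild, moderate, severe) and by causality (related, not related) to IP". It gives no rule for an event without a grade.

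SAP section 8.4.1 supplies the rules:

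- Counting: "participants will be counted only once within each SOC and PT at the maximum severity".
- Missing severity: "an AE with missing severity will be omitted from severity presentation and will not be imputed".
- Missing relationship: "an AE with relationship missing is treated as related".
- Missing seriousness: not imputed. Nothing is said about removing the event from a table.

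The overall TEAE summary in the same section lists "TEAEs by maximum Severity (severe>moderate>mild"), and repeats that breakdown for related TEAEs. It names three grades and no missing category. The SOC/PT tables by maximum severity, and by maximum severity and relationship, follow the same scheme.

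On collection, Protocol section 12.2.5 says that for each AE "the investigator will evaluate and report the onset (date and time), resolution (date and time), intensity, causality, action taken" and other attributes. A grade is therefore expected for every event.

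**The concern.** The severity tables are a breakdown of the TEAE counts. A reader expects the mild, moderate and severe rows to add up to the participants with any TEAE, and the related-by-severity rows to add up to the participants with a related TEAE. Under the omission rule they need not, and no row or footnote is specified to explain the gap.

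The direction also matters. Removing an event can never raise a participant's displayed maximum; it can only leave it unchanged, lower it, or take the participant out of the table. The SAP plans no hypothesis tests on safety (section 8.4), so these descriptive counts are what a reader uses to judge tolerability. One missing participant is most visible where counts are low.

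Relationship, handled in the same paragraph, goes the other way: a missing value is resolved conservatively and the event stays in the table.

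**Working it through.** The plan states no figure to reproduce here. The check applies the written rules to simple cases, and then to an illustration with assumed missing rates.

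**Step 1: cases.** Take one participant within one SOC/PT, drop ungraded events, and count at the highest remaining grade.

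| Recorded grades | Shown as | Error |
|---|---|---|
| ungraded only | no severity row | participant is in the any-TEAE row but in no grade |
| mild, ungraded | mild | too low if the ungraded event was moderate or severe; otherwise none |
| severe, ungraded | severe | none |

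For each participant the displayed maximum is right, too low or absent. This is not the same as every row being too low. In the second case, if the ungraded event was truly severe, the mild row is one too high and the severe row one too low.

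**Step 2: reconciliation.** A participant with only ungraded events is in the any-TEAE row and in none of the three severity rows. If such an event is related, or has a missing relationship and is therefore counted as related, the participant is in the related-TEAE row but in none of the related-by-severity rows. Either way the breakdown falls short of its parent row.

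**Step 3: illustration.** Assume a participant has *k* TEAEs in one SOC/PT, exactly one of them truly severe, and that each grade is missing independently with probability *m*. The documents give no value for *m*, so 1%, 5% and 10% are assumed.

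- P(no severity row) = m^k
- P(shown at a lower grade) = m × (1 − m^(k−1))
- The sum is m, the chance that a truly severe case is lost from the severe row.

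| m | k | No row | Lower grade | Lost from severe row |
|---|---|---|---|---|
| 1% | 1 | 1% | 0% | 1% |
| 1% | 2 | 0.01% | 0.99% | 1% |
| 5% | 1 | 5% | 0% | 5% |
| 5% | 2 | 0.25% | 4.75% | 5% |
| 10% | 1 | 10% | 0% | 10% |
| 10% | 2 | 1% | 9% | 10% |

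For *m* = 5% and *k* = 2: 0.05² = 0.0025, and 0.05 × (1 − 0.05) = 0.0475, together 0.05. With repeated events, most of the loss is under-grading, which a 'Missing' row alone would not reveal. That is why the fix also needs a footnote.

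**Step 4: scale.** Protocol section 13.8 plans 89 randomized per arm. If the Safety Set were that size, one affected participant would move a severity row by 1/89 = 1.1 percentage points. The actual denominator is the Safety Set, which may be smaller.

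**The case against.** The strongest reply is that this is a disclosed, prespecified convention in a descriptive table. Monitoring under Protocol section 14.1 includes source data verification and a check that AEs are properly documented on the eCRF, so there may be no ungraded events at all. This stands as a limit on size. It does not defend the rule: if no grades are missing, the fix changes nothing, and if some are, the present rule hides them from the table.

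A second reply is that relationship is the exception, since missing seriousness is not imputed either, and a worst-case rule is gentler for a two-level field than for a three-level one. This also stands. The contrast with relationship shows different treatment, not an error in itself. It tells against coding ungraded events as severe, which would report severe events that no investigator assessed.

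A reader might infer more than the documents support:

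- *That the safety endpoint is affected.* It is not. The endpoint is the proportion with any TEAE and does not use severity. Ungraded events stay in the overall TEAE counts, the SOC/PT incidence tables and the listings.
- *That SAP section 8.1 requires a missing row and section 8.4.1 contradicts it.* Section 8.1 says "The missing category will be omitted if there are no missing values for that variable", which might suggest a row whenever values are missing. The sentence before it says "A missing category shall be included only for categorical variables where no data is available", which is too unclear to establish a conflict. A specific AE rule would in any case normally prevail over a general one.
- *That the loss will differ between arms.* Nothing in the documents links ungraded events to early loss of participants or to one arm. The point does not depend on it.

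**Conclusion.** The concern holds as a minor, inexpensive improvement. By the SAP's own wording, the maximum-severity and severity-by-relationship tables can understate a participant's severity or leave the participant out, and they need not reconcile to their parent rows. This follows from the omission rule and the once-per-participant counting rule, without any assumption about rates.

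The size is unknown and probably small, because grading is mandatory. The 1% to 10% loss from the severe row rests on assumed missing rates, on independence between events, and on a single truly severe event per participant and SOC/PT. The lower limit is no effect. No endpoint, test or efficacy conclusion is involved.

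**What to change.** In SAP section 8.4.1, replace the omission rule with two elements:

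1. A 'Missing' severity row in the maximum-severity and severity-by-relationship tables, for participants whose only events in that SOC/PT are ungraded. In the overall summary, including its related-TEAE breakdown, the row holds participants for whom every TEAE being counted is ungraded. The rows then add up to the any-TEAE and related-TEAE rows.
2. A footnote with the number of participants shown at a known grade who also have an ungraded event. This covers the mild-plus-ungraded case.

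Neither element imputes anything or can overstate severity. Counting ungraded events as severe could be offered as an optional sensitivity display, but should not be the main rule.

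The cost is a short SAP edit, ideally before the Part 1 database lock, plus one extra table row and a footnote. If no grades are missing, the row can be dropped.

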### **13.6.2. Clinical Laboratory Evaluations**

Clinical laboratory assessments will include blood samples for hematology, clinical chemistry, and urinalysis. Samples will be collected  $\leq 2$  hours prior to dosing on dosing days. On non-dosing days, collection may occur at any time.

Results of clinical laboratory parameters in each scheduled visit and mean changes from baseline will be summarized in standard units. Normal ranges for each parameter will be provided by the laboratory; shift from baseline to postbaseline values in abnormality of results will be provided. Potentially CS values will be summarized by treatment. Clinical laboratory results will be listed by participant and timing of collection.

### **13.6.3. Physical Examinations**

A full physical examination is to be conducted during Screening and at Day 112. At other visits, physical examinations will include a brief assessment of general appearance, cardiovascular, respiratory, gastrointestinal, and neurological systems and followed by a targeted physical assessment as needed. A symptom-directed examination may be conducted at any time at the discretion of the investigator. The occurrence of a physical examination (yes/no) and the date performed will be listed by participant.

### **13.6.4. Vital Signs**

Vital signs will include body temperature, respiratory rate, heart rate, and blood pressure. Heart rate and blood pressure to be collected in supine position and standing position at all scheduled time points. Vital sign results at each visit and mean changes from baseline will be summarized by scheduled visit. Potentially CS values will be summarized by treatment. Vital sign results will be listed by participant and timing of collection.

### **13.6.5. 12-Lead Electrocardiogram**

A single ECG will be measured after the participant has been in the supine position for at least 5 minutes. The following ECG parameters will be listed for each participant: heart rate, PR, QRS, QT, and QTcF. ECG data will be summarized by visit. Potentially CS values of QTcF will be summarized by treatment. ECG findings will be listed by participant and visit.

### **13.6.6. Prior and Concomitant Medications**

Medications will be recorded at each study visit during the study and will be coded using World Health Organization-Drug dictionary (WHO-DD) September 2015, or later.

All medications and supplements taken within 8 weeks prior to Screening, all medications used to treat HD (including ASO therapies) regardless of timing, and all nonpharmacological methods (eg, psychosocial, psychotherapeutic) used to treat or prevent neuropsychiatric, functional, and cognitive manifestations of HD will be recorded. Those medications taken prior to the initiation of the start of IP will be denoted “Prior”. Those medications taken prior to the initiation of the IP and continuing beyond the initiation of the IP or those medications started at the same time or after the initiation of the IP will be denoted “Concomitant”. Medications will be presented according to whether they are “Prior” or “Concomitant” as defined above. If medication dates

are incomplete and it is not clear whether the medication was concomitant, it will be assumed to be concomitant.

Details of prior and concomitant medications will be listed by participant, start date, and verbatim term.

**13.6.7.** [REDACTED]

[REDACTED]

**13.6.8.** [REDACTED]

[REDACTED]

**13.6.9. Other Safety Analysis**

Not applicable.

**13.7.** [REDACTED]

[REDACTED]

**13.8. Sample Size and Power**

The study is designed to detect a difference between the placebo and SAGE-718 group in the change from baseline to Day 84 for the primary endpoint, SDMT score. Using a 2-sided test at an alpha level of 0.05, a sample size of approximately 71 evaluable participants per treatment group would provide 90% power to detect a difference of 4 points between the SAGE-718 and placebo arms in the change from baseline to Day 84 in SDMT values, assuming that the SD of the change from baseline in SDMT is 7.3 points.

Assuming a 20% dropout and a 1:1 randomization ratio, approximately 178 randomized participants (89 per treatment group) will be required to obtain 71 evaluable participants per treatment group. Evaluable participants are defined as those randomized participants who receive IP and have a valid baseline and at least 1 postbaseline SDMT assessment. Additional participants may be randomized to ensure a sufficient number of evaluable participants or if the dropout rate is higher than 20%.

## **14. DIRECT ACCESS TO SOURCE DATA/DOCUMENTS**

### **14.1. Study Monitoring**

Unless otherwise waived or addressed in another forum (eg, investigator meeting), before an investigational site can enter a participant into the study, a representative of Sage Therapeutics will visit the investigational study site to:

- Confirm the adequacy of the facilities
- Discuss with the investigator(s) and other personnel their responsibilities with regard to protocol adherence, IP management, GCP/ICH GCP compliance, and the responsibilities of Sage Therapeutics or its representatives. Agreed upon site responsibilities will be documented in a Clinical Trial Agreement between Sage Therapeutics and the investigator.

During the study, a monitor from Sage Therapeutics or representative will have regular contacts with the investigational site, for the following:

- Provide information and support to the investigator(s)
- Confirm that facilities remain acceptable
- Confirm that the investigational team is adhering to the protocol, that data are being accurately recorded in the eCRF, and that IP accountability checks are being performed
- Perform source data verification. This includes a comparison of the data in the eCRF with the participant's medical records at the hospital or practice, and other records relevant to the study. This will require direct access to all original records for each participant (eg, medical records, source documents, clinic charts).
- Record and report any protocol deviations not previously sent to Sage Therapeutics.
- Confirm AEs and SAEs have been properly documented on eCRFs and confirm any SAEs have been forwarded to Sage Therapeutics and those SAEs that met criteria for reporting have been forwarded to the IRB or IEC.

The monitor will be available between visits if the investigator(s) or other staff needs information or advice.

